#### **5.2.4. Early Withdrawal / Removal of Patients from Treatment**

Any patient may withdraw from the study at any time, without prejudice to their ongoing dental care. If a patient fails to attend a scheduled follow-up visit, the investigator (or designee) will attempt to contact the patient to reschedule the appointment and document the reason for non-attendance.

If a patient states that he/she no longer wishes to participate, the reason for withdrawal will be recorded whenever possible (e.g., lack of interest, relocation, change of dentist, adverse event). Patients will be reminded of the importance of attending follow-up visits for their own clinical care and to allow collection of safety data.

Alternative treatment options appropriate for the patient's condition will be offered in case of withdrawal before treatment completion.

The investigator may withdraw a patient from the study in the following cases:

- Non-compliance with the protocol requirements.
- Repeated failure to attend follow-up visits.
- Development of a medical condition, SAE, or AE which, in the opinion of the investigator, contraindicates further participation.
- Identification of a new exclusion criterion (or one not previously recognized) that precludes continued participation.
- Withdrawal of informed consent.

The investigator must withdraw any patient in case of tooth loss or if the site becomes unsuitable for evaluation of the primary endpoint.

All patient withdrawals will be documented in the study termination case report form (eCRF), including the reason for withdrawal. Whenever possible, the investigator will make every effort to collect the primary endpoint data (CRC at 12 months) prior to final withdrawal.

In case of premature study withdrawal after surgery, the patient will continue to receive follow-up care according to current clinical practice.

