### 5.1.1. Endpoints

#### 5.1.1.1. Primary Endpoint

**Complete Root Coverage (CRC)** at 12 months, defined as the proportion of treated recession sites presenting Recession Depth (RD) = 0 mm relative to the cemento-enamel junction (CEJ). Measurements will be performed with a CP-15 calibrated periodontal probe by a blinded examiner, using the CEJ as a fixed reference point.

Photographic documentation will be standardized using the same digital camera model, lens, and magnification settings. All images will be taken at a fixed distance with the aid of a custom acrylic stent and include a millimeter scale for calibration. Consistent lighting and angulation will be maintained across all time points to ensure reliable visual assessment of root coverage.

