### 5.2.2. Exclusion Criteria

- Patients will be excluded from participation if they meet any of the following criteria:
- Uncontrolled systemic diseases or conditions that contraindicate periodontal surgery (e.g., uncontrolled diabetes mellitus ( $\text{HbA1c} \geq 7.0$ ), severe cardiovascular disease, immunodeficiency).
- Pregnant or breastfeeding women.
- History of autoimmune disease or current immunosuppressive therapy.
- Known hypersensitivity or allergy to hyaluronic acid or any component of the investigational product.
- Heavy smokers ( $>10$  cigarettes/day) or users of smokeless tobacco/nicotine products within the last 6 months.
- Untreated periodontal disease or presence of probing depth  $\geq 4$  mm with bleeding on probing at the study tooth.
- Caries, non-carious cervical lesions, root fractures, defective restorations, or endodontic lesions in the study tooth.
- History of mucogingival surgery or previous root coverage procedure at the study tooth.
- Use of systemic antibiotics, corticosteroids, or anti-inflammatory drugs within 3 months prior to surgery (unless considered safe by the investigator).
- Coagulation disorders or current use of anticoagulant/antiplatelet medication that cannot be discontinued for surgery.
- Hormonal disorders significantly affecting wound healing.
- Active acute infections or inflammatory processes in the oral cavity at the time of surgery.

- Any medical, psychological, or social condition that, in the opinion of the investigator, could interfere with study participation or adherence to the follow-up schedule.

Patients may be informed about the study by any member of the department. However, after verifying the inclusion and exclusion criteria, the principal investigator will ultimately validate the patient's inclusion in the study.

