### **5.3. Study treatment**

#### **5.3.1. Concomitant Interventions**

Any concomitant Interventions at the intervention area of the study are allowed and must be recorded (date and specify intervention).

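### Section 5.2.4 lets patients whose site is still measurable leave after surgery without a 12-month root-coverage reading; secondarily, a site re-grafted before month 12 would literally count as a success

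*Protocol*

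**What the plan says.** **Withdrawal.** Protocol 5.2.4 lists grounds on which the investigator may withdraw a patient. They include "Non-compliance with the protocol requirements", repeated missed visits, and "Identification of a new exclusion criterion (or one not previously recognized) that precludes continued participation". Adverse events or medical conditions and withdrawal of consent are also listed. Separately, withdrawal is compulsory in one situation: "The investigator must withdraw any patient in case of tooth loss or if the site becomes unsuitable for evaluation of the primary endpoint".

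On the primary endpoint the section says: "Whenever possible, the investigator will make every effort to collect the primary endpoint data (CRC at 12 months) prior to final withdrawal". On what follows it says: "In case of premature study withdrawal after surgery, the patient will continue to receive follow-up care according to current clinical practice". Section 5.2.4.1 adds that data from patients who withdraw after randomisation are analysed by intention to treat as far as possible.

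**Re-treatment.** Section 5.3.1 reads: "Any concomitant Interventions at the intervention area of the study are allowed and must be recorded (date and specify intervention". The primary endpoint in 5.1.1.1 is CRC at 12 months, defined as "the proportion of treated recession sites presenting Recession Depth (RD) = 0 mm relative to the cemento-enamel junction (CEJ". Neither section mentions a second root-coverage operation.

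**The concern.** Non-compliance, missed visits and a late-found exclusion criterion are reasons to question a patient's adherence or eligibility. They do not stop an examiner from placing a probe at month 12. The section nevertheless ties collection of the 12-month outcome to a moment before withdrawal. For a patient withdrawn at, say, month 5, that instruction cannot be carried out unless withdrawal is held open for seven months, which the section does not say. After withdrawal no study visit is kept.

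This is a rule about conduct, so its effect is permanent. An analysis plan can choose how to treat missing values, but it cannot create readings that were never taken. The same visit also supplies the 12-month values for mean root coverage, recession reduction, attachment and probing changes and the esthetic score, so these go too.

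The secondary point is about meaning. A failed first operation that is re-grafted and then reads no recession at month 12 satisfies the endpoint as written, although the success belongs to the second operation.

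**Working it through.** **1. The plan's own figures (5.2.3).** Planning CRC rates are about 80% and 33%, with 15 evaluable per group, two-sided α = 0.05 and 80% power. The unpooled normal approximation gives n = (1.960 + 0.842)² × (0.80×0.20 + 0.33×0.67) / 0.47² = 13.5, so 14 per group, close to the stated 15. Allowing for 10% loss, 30 / 0.90 = 33.3, so 34 enrolled, as stated. The allowance is 34 − 30 = 4 patients, or two per arm. The sample size is not in question here; it shows how few patients carry the result.

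**2. Can 5.2.4 be followed as written?**
- The outcome exists only at month 12 (5.1.1.1).
- Withdrawal on the listed grounds may happen at any time after surgery.
- The outcome is to be collected before final withdrawal.
- After withdrawal, care follows current practice and no T7 reading is scheduled.

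For a withdrawal before month 12, the third line asks for a value that does not yet exist and the fourth closes the route to it. Intention to treat under 5.2.4.1 then has no outcome to analyse.

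**3. Size: unread patients.** The Protocol names no primary test, so a two-sided Fisher test is assumed. With n₁ and n₂ patients, K successes and N = n₁ + n₂, P(X = x) = C(n₁, x) C(n₂, K − x) / C(N, K). The p-value sums all terms no larger than the observed one. The counts are invented for illustration.

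- All read, 12/17 versus 6/17 (difference 35 points): p = 2 × (0.03475 + 0.00668 + 0.00073 + 0.00004) = 0.084.
- Two test-arm failures unread, 12/15 versus 6/17 (45 points): upper tail 0.01194 + 0.00138 + 0.00008 = 0.01340; lower terms 0.00197 + 0.00013 = 0.00210; p = 0.016.
- The opposite direction is just as possible. All read, 13/17 versus 6/17: p = 0.037. Two control failures unread, 13/17 versus 6/15: upper tail 0.03429 + 0.00588 + 0.00053 + 0.00002 = 0.04072; lower terms 0.02547 + 0.00374 + 0.00027 + 0.00001 = 0.02949; p = 0.070.
- A smaller loss does less. If the observed result is 12/15 versus 5/15 (p = 0.025), restoring one unread patient in a single arm gives p between 0.011 and 0.032, whatever that patient's outcome.

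**4. Size: re-grafted sites.** Same test, starting from the planning rates.

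| Re-grafted site | Counted as failure | Counted as CRC |
|---|---|---|
| One in control | 12/15 v 5/15, p = 0.025 | 12/15 v 6/15, p = 0.060 |
| One in test | 11/15 v 5/15, p = 0.066 | 12/15 v 5/15, p = 0.025 |

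The direction depends on which arm is re-treated, and the documents give no basis for predicting that.

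**The case against.** **The intent is to obtain the reading.** Section 5.2.4 asks for every effort, requires contact and rescheduling after a missed visit, and has patients reminded why follow-up matters; 5.2.4.1 invokes intention to treat. One could read the collection sentence as holding final withdrawal open until month 12. This shows that losses are permitted, not intended. But the section does not say that withdrawal is held open, and its next provision moves the patient to usual care.

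**The sizes are illustrations.** The test is assumed, event rates are unknown, about 10% loss is already budgeted, and sensitivity to one or two patients is common to any trial with 15 to 17 per arm. All of that stands. It limits the weight of the point but does not make the lost readings recoverable.

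**Re-treatment is not named and could be scored in an analysis plan.** Section 5.3.1 requires the date and type to be recorded, which would let a plan score the site as a failure. That is a fair answer on scoring, and it is why this half is secondary. It does not cover deferral: once a site is re-grafted, the first operation's 12-month result cannot be observed.

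**Stronger readings that the documents do not support.** A reader might infer that the investigator may choose between counting a re-grafted site as a success and withdrawing the patient under the exclusion "History of mucogingival surgery or previous root coverage procedure at the study tooth". That criterion concerns eligibility at baseline; after surgery every operated patient would meet it, so it cannot sensibly serve as a later ground. Withdrawal of an unsuitable site is compulsory, not optional; what is missing is a definition of unsuitable. A reader might also infer that an unblinded person steers withdrawals. Section 7.1 says that the surgeon is unblinded and the assessors are blinded, but nowhere does the Protocol say that the surgeon decides withdrawals. That inference rests on silence.

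**Conclusion.** The main point holds. Followed as written, 5.2.4 loses 12-month primary readings from operated patients whose site could still be measured, and neither 5.2.4.1 nor an analysis plan can restore them. The secondary point holds in a limited form: 5.3.1 and 5.1.1.1, read literally, count a re-grafted site without recession as a success of the first operation.

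The likely size is modest. Two unread patients in one arm, within the planned allowance of four in total, can move an illustrative result across 0.05 in either direction; one unread patient in one arm did not do so from the planning rates. These figures rest on an assumed Fisher test and invented counts. Event rates are not given and are probably low, and the direction of bias is unknown. The documents do not show that the trial is biased. The reason to act is that the loss is avoidable and cheap to prevent, provided the rule is in place before patients reach these points.

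**What to change.** **In 5.2.4:** state that patients withdrawn after surgery, for any reason other than withdrawal of consent or tooth loss, are still invited to the T7 recession-depth reading by the blinded examiner. In the sentence on collecting the primary endpoint, replace the words that place collection before final withdrawal with *at T7*. The cost is a few extra visits. Some patients who repeatedly miss visits will still not attend, so the rule reduces the loss without removing it.

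**In 5.3.1 and 5.1.1.1:** state that repeat root-coverage surgery at the study tooth is deferred until after the T7 reading where clinically acceptable, and that a site re-treated earlier counts as CRC not achieved. The cost is slightly lower CRC rates and a possible wait for some patients.

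The sample size need not change on this account.

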##### **5.2.4.1. Procedures for Replacement of Patients**

Patients who withdraw from the study after randomization will not be re-enrolled. Their data will be included in the analysis following the intention-to-treat (ITT) principle whenever possible.

If a patient withdraws during the enrolment phase and prior to surgery, the investigator will make all reasonable efforts to recruit a new eligible patient in order to maintain the planned sample size (30 patients, 15 per group). This approach is intended to preserve the statistical power of the study and the validity of the comparative analysis between the test and control groups.

#### **5.2.5. Screening Failures**

Any patient that has signed the informed consent form and does not receive the study product is considered a screening failure. In the event of a screening failure, the eCRF page should be completed up to the visit when the patient was determined to be a screening failure. The study termination eCRF page should also be completed.

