## **2. STUDY PRODUCT DESCRIPTION**

The investigational product is hyaDENT BG®, a sterile, transparent, highly viscous gel containing highly purified hyaluronic acid of non-animal origin with specifically adjusted molecular weight.

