## **2.3. Device Accountability**

The Investigator must maintain an accurate and up-to-date accountability record of all hyaDENT BG® cartridges received, used, discarded (opened but unused), and returned throughout the duration of the study. This information shall be documented in the Study Product Accountability Log, including product name, lot number, expiration date, date of use, and patient identification code.

At each monitoring visit, the study monitor will verify the completeness and accuracy of the accountability records and cross-check them with source documentation. At study close-out, the monitor or designated delegate will ensure full reconciliation of all investigational product units, confirming that all cartridges have been either used, appropriately discarded, or returned to the sponsor according to Good Clinical Practice (GCP) requirements

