### 5.2.3. Sample Size

This randomized, controlled PMCF study will enroll a total of 34 patients, allocated 1:1 to:

- **Test group (n = 17):** CAF + SCTG with adjunctive hyaDENT BG®
- **Control group (n = 17):** CAF + SCTG without hyaDENT BG®

The slight increase from the initially planned 30 patients is intended to accommodate an approximate 10% drop-out rate, ensuring that about 30 patients (15 per group) complete the study as evaluable. The sample size calculation remains based on the primary endpoint (CRC at 12 months) with 30 evaluable patients, while the additional 4 subjects provide a margin of safety for potential losses to follow-up.

The sample size was determined to reliably detect a clinically meaningful difference in the primary outcome. Previous randomized studies (e.g. Pilloni et al. 2019) have reported CRC rates of roughly 80% with CAF+HA versus 33% with CAF alone, an absolute difference of ~47 percentage points. Using this large effect size (47 pp), a two-sided  $\alpha = 0.05$ , and power ( $1-\beta$ ) of 80%, a minimum of 15 patients per group was deemed sufficient to demonstrate a statistically significant difference in CRC. By enrolling 17 per group (34 total), the study preserves this power assumption while accounting for possible drop-outs, thereby maintaining at least 15 analyzable subjects in each arm.

**Sensitivity Analysis of Power:** The sample size is powered to detect a large CRC difference (47 pp), based on prior data. However, if the true effect is smaller (e.g. 20–30 pp), the study may be underpowered to reach statistical significance. This highlights a potential risk of type II error for modest but clinically relevant differences. Exact power estimates for these scenarios will be calculated by the statistician using final parameters. Overall, the sample size represents a practical balance between feasibility and detecting a meaningful effect

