## **7. CLINICAL TRIAL**

### **7.1. Sample Size and Randomization**

Each patient will be randomly assigned to one of the two study groups (test or control) in a 1:1 ratio. The randomization sequence will be generated using a computer program (e.g., IBM SPSS) with stratification by recession type (Cairo classification RT1 vs RT2) and using permuted

blocks of random sizes. This stratified, blocked randomization ensures that patients with RT1 and RT2 recession defects are equally balanced across the two groups, preventing any imbalance in baseline recession severity. Allocation concealment will be maintained through the use of opaque, sealed, sequentially numbered envelopes. An independent investigator (not involved in the treatment) will open the next envelope in sequence immediately after flap elevation, thereby revealing the group assignment. The treating surgeon will thus be unblinded at the point of graft placement (since they must know whether to apply the HA gel), but the patients will not be explicitly informed of their group allocation. (Patients might potentially guess their group based on postoperative symptoms or the presence of the HA application, so complete patient blinding cannot be guaranteed; however, all outcome assessors remain fully blinded to group assignment.)

Based on the sample size calculations and previous study data, approximately 17 patients per group (34 total) will be enrolled in this trial. This enrollment target includes a buffer for potential drop-outs, with the goal of ending up with at least 15 evaluable patients in each arm at study completion. The groups are defined as follows:

- **Test group (n ≈ 17):** CAF + SCTG with adjunctive hyaDENT BG® (HA applied at the recipient site).
- **Control group (n ≈ 17):** CAF + SCTG without the adjunctive hyaDENT BG® (no HA application).

By employing stratified randomization and concealing the allocation, the study design mitigates selection bias and ensures that both groups are comparable with respect to key prognostic factors (notably the recession type). The 1:1 allocation with an effective sample of ~30 completers (15 per group) provides sufficient power to detect the expected difference in the primary endpoint, while the slight over-enrollment to 34 accounts for attrition and preserves statistical integrity.

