#### Surgical technique:

- Local infiltrative anesthesia (2% lidocain with epinephrine at a concentration of 1:100,000)
- Incision design is performed with a microblade (USM-6700) or with a 15c blade
- After flap preparation, a gentle root planing is performed using gracey curettes /mini-five
- Coronal advanced flap is obtained by cutting the superficial muscle fibers using a blade parallel to the external surface of the mucosa.
- Anatomical papillae are de-epithelialized with the scalpel blade and microsurgery scissors.
- The width of the graft was chosen according to the amount of tissue required to cover the exposed root and 3 mm of connective tissue mesial and distal to it.
- Immediately after harvesting, the subepithelial connective tissue graft (SCTG) is placed in a sterile dish
- In the test group, the SCTG is completely immersed (fully soaked) in sterile hyaluronic acid gel
- The graft remains immersed for approximately 1–3 minutes to ensure full surface contact and to prevent dehydration
- Excess hyaluronic acid is allowed to drain passively without compression prior to graft placement

- In the control group, the SCTG is maintained under sterile conditions and hydrated with sterile saline solution for a comparable time interval, without contact with hyaluronic acid

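### Screening failure is defined by receipt of the gel, not by randomisation, so a patient randomised to test but not given hyaDENT BG can drop out of data collection in one arm only

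*Protocol*

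**What the plan says.** Section 5.2.5 of the protocol gives the rule: "Any patient that has signed the informed consent form and does not receive the study product is considered a screening failure". It then sets the consequence for data capture, namely that "the eCRF page should be completed up to the visit when the patient was determined to be a screening failure", and asks for the study termination page as well.

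Section 2 fixes what the study product is: "The investigational product is hyaDENT BG®, a sterile, transparent, highly viscous gel". Sections 2.3 and 2.4 use the term in the same sense. The Study Product Accountability Log is an "accurate and up-to-date accountability record of all hyaDENT BG® cartridges received, used, discarded (opened but unused), and returned", and the return of study product concerns those cartridges only.

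Controls do not receive it. Under Surgical technique in section 7.4 their graft is "hydrated with sterile saline solution for a comparable time interval, without contact with hyaluronic acid".

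Section 5.2.3 says that the study "will enroll a total of 34 patients, allocated 1:1 to" the two groups, 17 in each. Section 7.1 has the allocation envelope opened straight after flap elevation. Sections 2.2.2 and 7.4 place the use of the gel later in the same operation, once the graft has been harvested.

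For patients who withdraw after randomisation, section 5.2.4.1 says: "Their data will be included in the analysis following the intention-to-treat (ITT) principle whenever possible".

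**The concern.** In a randomised trial, screening ends when the patient is allocated. A screening-failure rule should therefore depend only on what happened before allocation. Section 5.2.5 depends instead on exposure to the test product, which is settled after allocation and is possible in one arm only.

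For a control, not receiving the gel is the assigned treatment. For a test patient, it is a departure from the assigned treatment that happens after randomisation. A site that applies the rule to that test patient closes the record at surgery, so no 12-month outcome is collected. A control with the same course up to that moment is followed for the full year. The comparison then no longer rests on everyone randomised, in a trial where each patient carries several percentage points of the primary endpoint.

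**Working it through.** **1. The planned numbers.** Section 5.2.3 takes 15 evaluable patients per group and allows for about 10% drop-out: 15/(1 - 0.10) = 16.7, rounded up to 17 per group, and 30/(1 - 0.10) = 33.3, rounded up to 34 in total. Both match the stated enrolment.

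**2. The rule applied word for word.**
- Study product = hyaDENT BG (sections 2, 2.3 and 2.4).
- Controls receiving it, by design: 0 of 17 (sections 7.1 and 7.4).
- Screening failures on the wording: 17 of 34 = 50% of enrolment, plus any test patient not given the gel.

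No section extends the term study product to the control procedure, and none confines the rule to the time before randomisation.

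**3. Can a patient be randomised to test and not receive the gel?** The order of events is consent, flap elevation, envelope opened, graft harvested, gel applied. There is an interval between allocation and exposure. Section 2.2.2 itself foresees cartridges that may not be used because the packaging is opened or damaged. The protocol gives no expected frequency, so the effect is shown per patient.

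**4. Effect of one removal on the test-arm rate.** Inputs: test rate p = 0.80 (the figure used for planning in section 5.2.3) and n = 15 (evaluable) or 17 (enrolled) in the arm. Removing a patient also lowers the denominator:
- a failure removed: pn/(n - 1) - p = p/(n - 1)
- a success removed: (pn - 1)/(n - 1) - p = -(1 - p)/(n - 1)

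| n | Failure removed | Success removed |
|---|---|---|
| 15 | 0.80/14 = +5.7 points (12/15 to 12/14 = 85.7%) | -0.20/14 = -1.4 points (12/15 to 11/14 = 78.6%) |
| 17 | 0.80/16 = +5.0 points (80% to 85.0%) | -0.20/16 = -1.25, about -1.3 points (80% to 78.75%) |

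Against the planned difference of 47 points, one failure removed is 5.0/47 = 11% to 5.7/47 = 12% of the effect.

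**5. The definition moved to randomisation.** If a screening failure is a consented patient whose envelope was not opened, none of the 34 randomised patients is one. The arms stay at 17 and 17, and the sample size does not change.

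**The case against.** The strongest reply is that the sentence stands under a heading about screening, and that the protocol treats screening as a phase before surgery: sections 5.2.1 and 5.4 both separate the two. Sections 5.2.3, 5.5, 6.1 and 7.1 all describe a control arm that is followed and compared. On that reading the sentence means only patients who consent and never reach study treatment. This is very probably the intent, and it disposes of one inference that a reader might draw, that the 17 controls would actually be lost. The documents do not support that outcome, because every description of the design presumes a followed control arm.

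Second, section 5.2.5 governs eCRF pages and defines no analysis set. Analysis sets are commonly left to a statistical analysis plan, which is not at hand. That is correct, but it does not remove the problem: no analysis plan can recover 12-month data that the site was told not to record.

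Third, the event should be rare. Section 5.2.2 excludes known hypersensitivity beforehand, and section 2.2.4 puts two cartridges in each package. This also stands. It limits how often the rule would be triggered, not what happens when it is.

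Fourth, a reader might say that section 5.2.5 flatly contradicts section 5.2.4.1. That is too strong. Section 5.2.4.1 speaks of patients who withdraw, and a test patient not given the gel has not withdrawn. The conflict is with the intention-to-treat principle invoked there.

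**Conclusion.** The definition is wrong as written and should be corrected. Its literal effect on controls is a drafting fault that nobody is likely to act on. Its effect on a test patient who is randomised and then not given the gel is a real gap: the wording tells the site to stop the record, and nothing else in the protocol says otherwise.

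The size is +5.0 to +5.7 points on the test rate for each failure removed and -1.3 to -1.4 points for each success removed. This assumes the planned 80% rate and 15 to 17 patients in the arm. The direction cannot be known in advance, since it depends on the outcomes of the patients removed, and the protocol gives no basis for how many there would be.

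A reader might take one patient's simple weight, 1/17 = 5.9 to 1/15 = 6.7 points, as the shift. That overstates it at the planned rate, because removal also shrinks the denominator. The full 1/n is reached only when the patient removed is the arm's only failure or only success.

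**What to change.** In section 5.2.5, define a screening failure as a patient who signed consent but was not randomised, that is, whose allocation envelope was not opened. Word the eCRF instruction to match.

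Add one sentence: randomised patients remain in their assigned arm for data collection and for the intention-to-treat analysis whether or not hyaDENT BG was applied, subject to the withdrawal provisions of section 5.2.4. The qualification is needed because that section lets patients withdraw at any time and requires withdrawal after tooth loss, so follow-up of every patient to 12 months cannot be promised.

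The qualifier attached to the intention-to-treat statement in section 5.2.4.1 is a separate matter and need not change for this repair.

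The cost is one sentence replaced, one added, and the matching eCRF guidance. Sample size, visits and procedures are unaffected.
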